## 2. Methods

**2.1. Objectives** – HIV testing is the gateway to HIV prevention, treatment and HIV control, but uptake is suboptimal in South African men. Consequently, men have poor HIV outcomes including lower HIV testing uptake, lower ART initiation and a lower proportion achieving viral suppression. This study will investigate the effect of a participatory, user designed message to increase knowledge about U=U on HIV testing uptake in men in the Klipfontein Mitchells Plain (KMP) district in Cape Town, through a randomized trial design. The primary objectives of this study are 1) to develop a U=U message that encourages HIV testing uptake in men using a participatory, user-centered workshop, and 2) to investigate the effect of U=U messaging on HIV uptake in men. The primary outcome will be HIV testing uptake at a community-based mobile clinic. Secondary outcomes will include the proportion of males tested who are HIV-positive (and newly HIV positive).

**2.2. Study Duration and Setting** – The study will be 12 months in duration including the preparation period, Phase 1, Phase 2 and analysis. The study will take place in KMP, a resource-limited, densely populated, high HIV disease burden area in Cape Town, where the use of health services among men is sub-optimal. The DTHF Tutu Tester offers mobile HIV testing clinic days in various locations in the region, including KMP. Trained recruiters stationed at the Tutu Tester mobile clinic sites distribute invitation cards inviting men to visit the mobile clinic for a voluntary HIV test. The intervention will utilize the Tutu Tester to trial a new messaging intervention. DTHF will build upon their existing activities and relationship with the local community to implement this study in KMP. DTHF will complete all data collection. Penn will not take part in data collection, nor will Penn interact with the subjects.

**2.3 Inclusion criteria and recruitment** – Recruitment will be conducted by trained mobile clinic staff at selected high foot-traffic sites in the KMP community. Men in high HIV disease burden areas in KMP will also be recruited through community outreach activities to participate in the study. Inclusion criteria for the study will be males at least 18 years of age within the vicinity of the mobile Tutu Tester HIV testing van.

The study will consist of two phases:

### 2.4. Phase 1

**2.4.a. Design** – In phase 1, we will develop a U=U message using a participatory, human-centered design framework. There is increasing recognition that intervention design should incorporate viewpoints from the target audience to enhance collaboration, improve acceptability, and increase uptake (Byrne & Sahay, 2007; Mabunda, Khoza, Van den Borne, & Lebese, 2016). Thus, this participatory research will include workshops of approximately 40 men from a population that may potentially be recipients of the intervention.

**2.4.b Process** – Mobile clinic staff will invite approximately 20 men from high traffic locations in the KMP region to participate in design workshops for the development of a U=U message, that even if HIV positive they can be untransmittable, to normalize HIV and mitigate the fears of testing HIV positive. Each workshop participant will be asked to give informed consent, and then a trained facilitator will present the U=U message to the participants and facilitate the group to develop a message that resonates with them in language that is sufficiently colloquial to enable easy understanding among local

men. Their suggestions and statements will be recorded in written form verbatim and used to generate the invitation message. Once developed, the message will be presented to approximately 5-10 more men from within the community who will be invited to rate and suggest improvements to the acceptability of the prototype message. Following this exercise, the message will be fine-tuned and the final message will be printed on invitation cards for the phase 2 randomized trial.

## 2.5. Phase 2

2.5.a. Design – In phase 2, a cluster randomized trial will be conducted to determine the effect of the U=U message on HIV testing uptake. Individual mobile clinic days (i.e., the tester being parked at one site for one day) will serve as the unit of randomization, with each site day being assigned to the treatment or control condition via a computer-generated randomization process. Randomization will be stratified by testing location so that an equal number of clinic days at each location within KMP are assigned to each study group. On each mobile clinic day during the study, men in the vicinity of the mobile clinic will be offered invitation cards for same-day testing. Invitation cards will have unique identification codes. The information content on the referral cards and the mobilization approach will vary depending on condition.

2.5.b. Intervention group – Following phase 1, the final U=U messages will be printed on invitation cards to be distributed at mobile testing sites. Messages will seek to assuage the fears of testing HIV positive by conveying the message that HIV treatment makes it possible for HIV positive people to be untransmittable and to live normal lives. Messages will encourage men to come in for HIV testing at the mobile clinic on the same day. A mobile clinic recruiter will deliver the invitation and share a brief script explaining U=U.

2.5.c. Control group – The standard invitation cards used at the Tutu Tester contain basic information encouraging HIV testing. Messages will encourage men to come in for HIV testing at the mobile clinic on the same day. A mobile clinic recruiter will deliver the invitation and share a brief script including the standard Tutu Tester message.

2.5.d. Study Instruments: Invitation cards – After mobile clinic recruiters deliver the invitation card and scripted verbal message, they will request the participant bring the card with them if they return to test. The card will contain the distribution date and time and recruiter information. The recruiter will also separately record the date and time the invitation was delivered, and whether the mobile clinic was visible on the card. When the participant returns to visit the mobile clinic, the recruiter will request the card and record the date and time of presentation as well as the unique identification code on the card. The participant will then be invited by a counsellor into a cubicle in the mobile clinic to complete a rapid HIV test after the counsellor consents the participant.

2.5.e. Study Instruments: Questionnaire – Key information will be collected from participants who come for testing via tablet. This intake will be completed immediately after an individual arrives at the Tutu Tester and presents their card. This will include a confirmation of inclusion criteria to ensure that the men are at least 18 years old. Other key information will include: type of message (intervention or control), line of sight, date and time of message delivery, date and time of presentation for HIV testing,

time taken to get tested, age, whether the participant brought a peer or partner, whether the person stayed for an HIV test or not and HIV status. Several open-ended questions to learn about men's perceptions of the U=U messaging may also be asked including: if they had any previous understanding of U=U, what they think about the message and how this might change their behavior. The DTHF team will translate and validate the questionnaire and confirm its cultural appropriateness. As per standard operating procedure, those who test HIV positive will receive post-test counselling and assessment by a nurse and will be referred to their preferred clinic facility for HIV treatment.

2.5.f. Sample size and power calculations – In phase 2, the DTHF Tutu Tester will circulate between approximately four different locations within KMP. The Tutu Tester will be based in only one location on any given day. Clusters will comprise men who receive invitation cards on the same clinic day. Power calculations assumed 8 percent HIV testing uptake among men in the control group (based on two operational pilots conducted by our team) and an intraclass correlation of 0.02. With 40 clinic days in the study and 100 men within the vicinity of the Tutu Tester receiving invitation cards on each clinic day, we will have 80 percent power to detect a difference in HIV testing between groups of at least 5 percentage points.

2.5.g. Outcomes and analysis – The primary outcome will be HIV testing uptake, measured at the Tutu Tester based on presentation of the invitation cards. A chi-squared test will be conducted to estimate the effect of the intervention on HIV testing uptake. Logistic regression models will also be estimated to control for location, time of day, and distributor effects. Additional outcomes examined will include the proportion of males tested who are HIV-positive (and newly HIV positive).

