Study setting and population:	KMP is a resource-limited, densely populated, high HIV disease burden area in Cape Town, where the use of health services among men is sub-optimal. Recruitment will be conducted by trained mobile clinic staff at high foot-traffic sites in the KMP community. Recruitment efforts will focus on young men in multiple mobile testing sites that are located in areas within KMP where there is a high burden of HIV.
Study size:	
In phase 1, approximately 20 men will be invited to participate in formative research through insight workshops for U=U message development. After the initial message development, about 20 more men will be invited to give feedback and suggest improvements to ensure understanding and acceptability of the messaging.
 
In phase 2, 40 clinic days will be randomized to intervention or control, with 100 men in the vicinity of the Tutu Tester receiving invitation cards for testing on each day (N=4,000).

Process:	In phase 1, mobile clinic staff will invite men to participate in an insight workshop at a community location. Men who agree to participate will respond to questions and take part in group brainstorming activities that will inform development of U=U messaging.

	
The research team will map the ideas and themes and use these to create an invitation to men. Their feedback will be used to calibrate the messages for the phase 2 trial.
 
In phase 2, a trained recruiter will deliver a U=U invitation message on intervention days and standard HIV testing messaging on control days to encourage HIV testing at a mobile clinic. On each day, recruiters will deliver about 100 invitation cards to young men in the vicinity of the mobile testing van where free HIV testing will be available.

Duration:	Phase 1 will run for one month. Phase 2 will run for 3 months.
Analysis:	In phase 1, acceptability will be measured through workshop feedback. In phase 2, a chi-squared test will estimate the effect of U=U messaging on HIV testing uptake compared with standard of care. We will also compare HIV positivity by study arm. Logistic regression analysis will model the effects of participant demographics, binary line of sight of mobile clinic, and time of day on testing uptake and time to presentation at the clinic.

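### Clinic days are balanced by location but not over time, and no model includes date or visit order, so chance early/late imbalance could add modest, avoidable error

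*Combined protocol and SAP*

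**What the plan says.** Section 2.5.a names one balancing factor, testing location: "Randomization will be stratified by testing location so that an equal number of clinic days at each location within KMP are assigned to each study" [...]. The sequence is to be generated by computer. Block sizes, visit order and the spacing of visits are not described.

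The synopsis says that "Phase 2 will run for 3 months", and section 2.5.f that "the DTHF Tutu Tester will circulate between approximately four different locations within KMP", so each site is visited repeatedly over that period.

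On analysis, section 2.5.g plans a chi-squared test for the primary outcome and adds: "Logistic regression models will also be estimated to control for location, time of day, and distributor effects". The synopsis also lists demographics and whether the van was in sight. Time of day is a within-day factor. Calendar date and visit number appear in none of these models, although section 2.5.d has the delivery date recorded for each card.

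**The concern.** Uptake at a site could change over repeated visits: willing men may be tested early, or recruiters may improve or tire. Location-only balancing fixes how many days each arm has at a site, but not whether they fall early or late. With few visits per site, the arms may differ by chance in average visit number, and any drift then passes into the arm difference. What is at stake is precision and power. The stated design has only a small margin above its 80% target, and the data needed to remove this error are already being collected.

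**Working it through.** **Inputs from section 2.5.f.** "Power calculations assumed 8 percent HIV testing uptake among men in the control group"; "an intraclass correlation of 0.02"; 40 clinic days with 100 cards each, hence 20 days and 2,000 men per arm; a 5-point difference (8% against 13%); 80% power; about four locations.

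**Assumptions, not in the documents.** Two-sided alpha of 0.05; an even spread of 40/4 = 10 visits per location, five per arm; linear drift of 0, 0.5 or 0.75 points per visit, which is 0, 9 × 0.5 = 4.5 or 9 × 0.75 = 6.75 points from first to tenth visit; drift added on top of the stated intraclass correlation.

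**1. The plan's own power.** The design effect is 1 + 99 × 0.02 = 2.98. With no message effect, the standard error of the arm difference is √(2 × 0.08 × 0.92 × 2.98/2000) = 1.48 points. At 8% against 13% it is √((0.08 × 0.92 + 0.13 × 0.87) × 2.98/2000) = 1.67 points. A t-test on clinic days (38 df) then has 83.2% power, and a two-sided z-test 84.9%. The difference detectable at 80% power is 4.65 to 4.81 points, depending on the formula, which rounds to the stated 5. The plan's figure is slightly conservative.

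**2. Chance imbalance in time.** Visit numbers 1 to 10 have variance 9.167. With a random 5/5 split, the difference in mean visit number has variance 9.167 × (1/5 + 1/5) = 3.667 within a site. Averaged over four sites it is 3.667/4 = 0.917, an SD of 0.96 visits.

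**3. Effect on the arm difference and power.** The added SD is drift × 0.957. It combines with the sampling error as a root sum of squares.

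| Drift per visit | Added SD (points) | SE, no message effect | SE at 8% vs 13% | Day-level power (t, 38 df) |
|---|---|---|---|---|
| 0 | 0 | 1.48 | 1.67 | 83% |
| 0.5 | 0.48 | √(1.48² + 0.48²) = 1.56 | √(1.67² + 0.48²) = 1.74 | 80% |
| 0.75 | 0.72 | √(1.48² + 0.72²) = 1.65 | √(1.67² + 0.72²) = 1.82 | 77% |

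**4. Bias and false positives.** Simulated trials (beta-binomial, 20,000 runs per setting, location-only allocation, sites visited in rotation) used total trends of 0 to 12 points over Phase 2. With no message effect, the mean estimate was 0.00 points throughout and a day-level t-test rejected in 4.9% to 5.4% of runs.

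**5. Adjusting for time, randomisation unchanged.** In the same simulations, adding location and a linear time term gave 82.0% to 82.6% power over trends of 0 to 12 points, with type I error of 4.7% to 5.2%. For drifts of 0 to 0.75 points per visit, a location-adjusted day-level model with visit number has about 82-83% power.

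**6. Blocking the allocation.**
- Blocks of 4, 4 and 2 within a site: a block of four contributes (4/3) × 5 = 6.667 to the variance of the summed difference, and a block of two contributes 2 × 0.5 = 1. The variance of imbalance is (2 × 6.667 + 1)/25/4 = 0.143, an SD of 0.38 visits.
- Strict pairs of consecutive visits: 5/25/4 = 0.05, an SD of 0.22 visits. The second day of each pair is then known in advance, so 50% of days are predictable, against about 17% under a 5/5 split per site. A paired test has 19 df and 81.2% power, against 83.2% with 38 df.
- Pairing the days but analysing them as unpaired makes the day-level test conservative: type I error 2.8% at an 8-point trend.

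**7. The chi-squared test, if it ignores clustering.** It rejects a true null in 25.3% of runs with no trend and 27.1% with a 4-point trend. With paired allocation it still rejects in 25.5% to 26.3%.

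**The case against.** The strongest reply is that this is ordinary chance imbalance, already covered by a valid test, and that its size rests on an invented drift. Much of that stands.

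- A reader might infer that a time trend could bias the result or pass for a message effect. The documents do not support this. Days are randomised, so early/late imbalance is equally likely in either direction, and a day-level test keeps its error rate near 5%.
- No document reports drift, site population or depletion. On an 8% base, 4.5 points is more than half of control uptake. Smaller drifts have smaller effects.
- The sample size already allows for day-to-day variation. An intraclass correlation of 0.02 at 8% implies a between-day SD of √(0.02 × 0.08 × 0.92) = 3.8 points, whereas a drift of 0.5 per visit has an SD of 0.5 × √8.25 = 1.4 points, about 14% of that variance. If 0.02 already includes drift, planned power is not eroded; adjustment would then be a gain in precision.
- A reader might also infer that pairing visits is free and removes time effects in general. It has the costs shown above, and its variance reduction (0.917/0.05, about 18-fold) holds only for a linear trend. Holidays or paydays fall on single dates, and if the van rotates among sites, consecutive visits to one site need not be adjacent days.
- The text is silent on time blocking and does not exclude it.

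What the reply does not answer is that no stated model uses date or visit order, and that adding it costs almost nothing.

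**Conclusion.** The point holds as a modest, cheaply avoided loss of precision, not as a source of bias. Under the stated assumptions, a drift of 0.5 points per visit raises the standard error by about 5% (1.48 to 1.56 points) and uses up the design's margin above 80% power. At 0.75 points per visit, power falls below the target, to about 77%. With no drift, nothing is lost except about one degree of freedom. The conclusion rests on an even spread of about 10 visits to each of four sites, a linear drift that the documents neither report nor rule out, and drift being additional to the stated intraclass correlation. It does not extend to isolated calendar shocks. It is also secondary to the handling of clustering in the primary test, because an unclustered chi-squared test would have a false-positive rate near 25% with no drift at all.

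**What to change.** **Section 2.5.g (main change).** Add visit number at the location, or calendar date, to a model that includes location and accounts for clustering by clinic day. Specify it before outcome data are examined by arm. Cost: about one degree of freedom; no extra days, men or data.

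**Section 2.5.a (clarification).** State how the sequence is generated and the block sizes, if any.

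**Section 2.5.a (optional).** Fix the site schedule first, then block the allocation over visit order within each location, for example in blocks of 4, 4 and 2, and include visit order or block in the analysis. Costs: some days become predictable to recruiters, who know the arm they deliver (half of all days if strict pairs are used); each location needs an even number of visits; and a strictly paired analysis loses about 2 points of power.

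Neither change replaces the need for a primary test that accounts for clustering.

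### Recruiters know the day's arm, and with no stated order of approach and no count of men approached or declining, the men who receive cards may differ by arm

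*Combined protocol and SAP*

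**What the plan says.** Section 2.5.a randomises mobile clinic days by computer: "Randomization will be stratified by testing location". It adds: "The information content on the referral cards and the mobilization approach will vary depending on condition". Under 2.5.b and 2.5.c the recruiter hands over the arm's own card and speaks the arm's own script, and no masking is described.

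Section 2.3 gives one eligibility frame for both arms: males aged at least 18 near the van, at selected high foot-traffic sites. The synopsis adds a focus on young men and about 100 cards a day.

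The analysed set is defined in 2.5.f: "Clusters will comprise men who receive invitation cards on the same clinic day". In 2.5.g: "The primary outcome will be HIV testing uptake, measured at the Tutu Tester based on presentation of the invitation cards".

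The card has a unique code and carries the hand-out date and time and recruiter information. In addition, "The recruiter will also separately record the date and time the invitation was delivered, and whether the mobile clinic was visible on the card" (2.5.d). Other participant data come later: "Key information will be collected from participants who come for testing via tablet" (2.5.e). Section 3.1 provides for recording reasons for non-participation, but in the consent text for men who present for a test, not for men who decline a card.

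On adjustment, 2.5.g says: "Logistic regression models will also be estimated to control for location, time of day, and distributor effects". The synopsis says: "Logistic regression analysis will model the effects of participant demographics, binary line of sight of mobile clinic, and time of day on testing uptake".

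**The concern.** Randomising days balances days. It does not balance a group of men that forms after the arm is known. Here the recruiter necessarily knows the arm, chooses whom to approach among eligible passers-by, and loses from view any man who declines. The target of about 100 cards nearly fixes how many men enter each cluster, but not which men.

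If recruiters, without intending it, approach different men on U=U days, or if different men accept, uptake per card can move in either direction with no effect of the message on any man's decision to test. The trial exists to attribute a difference to the message, so a reader would want to exclude this explanation. Hand-out times, recruiter, card codes and line of sight allow a partial comparison of the arms. Counts of men approached and declining cannot be recovered afterwards.

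**Working it through.** **Do the planned safeguards reach the problem?** Two men passing the same recruiter, at the same site and hour, with the van in view, have the same location, time, distributor and line of sight. Choosing one rather than the other changes none of these, so stratifying or adjusting on them cannot correct the choice. The synopsis also lists demographics, but they are collected only from men who come for testing. At the planned 8% uptake they would be missing for about 92% of card recipients, so they cannot adjust for who received a card.

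**Inputs from 2.5.f.** Control uptake 8%, ICC 0.02, 40 days of 100 men, hence 20 days and 2,000 men per arm. A two-sided 5% level is assumed, as none is stated.

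**The plan's own figure.** Design effect = 1 + 99 × 0.02 = 2.98. Effective n per arm = 2,000/2.98 = 671. For 8% against 13%, SE = √[(0.08 × 0.92 + 0.13 × 0.87)/671] = 1.67 points, and 5/1.67 = 3.00. Power is 83% (non-central t, 38 df) or 85% (normal). With a continuity correction and one day per arm held back it is 80.6%. The stated 80% is consistent with this.

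The rejection rates below use the same t calculation with clustering handled. They do not describe the plain chi-squared test that the plan names. The documents give no approach or refusal data, so every input on selection is an assumption, and the message is taken to have no effect.

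**A. Choice of whom to approach.** Take two equal groups of passers-by with 12% and 4% uptake, so that control uptake is 0.5 × 12 + 0.5 × 4 = 8%. If a share s of U=U-day cards goes to the keener group, uptake = 12s + 4(1 − s).

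| s | U=U-day uptake | Spurious difference | Chance of rejection (nominal 5%) |
|---|---|---|---|
| 55% | 8.4% | +0.4 | 6% |
| 60% | 8.8% | +0.8 | 8% |
| 70% | 9.6% | +1.6 | 17% |

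A tilt the other way changes the sign: s = 40% gives 7.2%, or −0.8 points. With less contrast between the groups (10% and 6%), shares of 60% and 70% give +0.4 and +0.8 points.

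**B. Card acceptance.** Take 80% acceptance on control days, so testers per man approached = 0.80 × 0.08 = 0.064. Take 70% acceptance on U=U days, and let r be the uptake that the extra 10% of decliners would have had. Uptake per card = (0.064 − 0.10r)/0.70.

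| r | Uptake per card | Difference | Chance of rejection |
|---|---|---|---|
| 0 | 9.14% | +1.1 | 11% |
| 4% | 8.57% | +0.6 | 7% |
| 8% | 8.00% | 0 | 5% |

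Section 2.5.d mentions the card before the script. If that order is followed, the script has little chance to change acceptance and the gap would be smaller. The order is not stated as a rule.

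**C. What a men-approached denominator would show.** In case B the control figure is 6.4%, and the U=U figure is 6.4% − 0.10r: 6.4%, 6.0% or 5.6% for r = 0, 4% or 8%. It removes the distortion when the extra decliners would never have tested. When they would have tested at the average rate, it shows a difference although the per-card comparison shows none. It cannot repair selective approach.

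**D. Precision of a tally.** Acceptance of 80% against 70% with 2,000 cards per arm means 2,500 and 2,857 men approached, or 125 and 143 a day. With an assumed ICC of 0.02, 0.05 or 0.10, the SE of the acceptance gap is 2.25, 3.25 or 4.44 points. Multiplied by 2.024, this is about ±4.5, ±6.6 or ±9.0 points.

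**The case against.** The strongest reply has three parts.

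First, the plan does say who is eligible, and says it identically for both arms. A reader might infer that recruiters have no rule at all. Section 2.3 does not support that; only an order of approach is missing.

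Second, 2.5.a openly lets the mobilization approach vary by condition. If that variation is part of the intervention, a different acceptance rate is partly the intervention at work. A reader might infer that any acceptance gap is spurious. The documents do not support that either, because they do not say whether the effect sought is per card taken or per man approached. This stands, and it limits case B. It does not touch case A, since choosing keener men is not described anywhere as part of the intervention.

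Third, the harm is conjectural. No refusal figure exists, nothing suggests that recruiters would choose differently by arm, and small departures barely matter: a 55% share of keener men gives 6% rejection against 5%. Location strata, scripted delivery, coded cards and the daily card target all help. This also stands, and it is why the point ranks low. It does not fill the gap, because none of these safeguards controls or records which eligible men were approached or declined.

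**Conclusion.** The point holds as an inexpensive improvement to conduct and reporting, of low severity (to consider). That recruiters know the arm is an inference, but a firm one, since they deliver the arm's card and script. The plan leaves open a route to selection after randomisation that its stratification and adjustments cannot close.

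Under the assumptions in A, a 60% or 70% tilt produces +0.8 or +1.6 points, against a design difference of 5 points. Under those in B, the distortion per card is 0 to +1.1 points, and whether to call it bias depends on the estimand. The true size and direction are unknown and may be near zero. A reader might infer that the trial's result would be biased; the documents show an unprotected route, not that bias occurs.

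**What to change.** In 2.5.d, state that in both arms recruiters approach the next apparently eligible man after each hand-out, and keep a daily tally, without personal data, of men approached and men declining. The approach rule is the part that addresses selective approach.

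In 2.5.g, state that the primary denominator is all cards issued, report approach and refusal counts by arm, and add uptake per man approached as a supporting analysis that does not correct the primary one.

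In 2.5.a, the sponsor should say whether any arm-specific approach before the card is accepted is part of the intervention. A common opening in both arms is an option, not a required change: it would make acceptance more comparable, but it narrows the intervention being tested.

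The cost is a few lines of protocol text, some recruiter training and a small recording burden. Unblinded recruiters would keep the tally, and it is coarse: at an ICC of 0.02 to 0.05 it could show an acceptance gap of about 10 points, but not a small one.

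### The arm-aware recruiter role supplies both the numerator and the denominator of the primary outcome; name a code-linked test record and a card count as the sources instead

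*Combined protocol and SAP*

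**What the plan says.** All references are to the combined protocol and SAP.

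- **Delivery.** Sections 2.5.b and 2.5.c have a mobile clinic recruiter hand over the card with a U=U script or the standard script. Under 2.5.d the recruiter also keeps a separate record of when each card was delivered and whether the van could be seen. The synopsis (Process) says "recruiters will deliver about 100 invitation cards to young men in the vicinity of the mobile testing van".
- **Presentation.** Under 2.5.d, when the man comes to the van, "the recruiter will request the card and record the date and time of presentation as well as the unique identification code on the card".
- **Outcome.** Section 2.5.g defines testing uptake as "measured at the Tutu Tester based on presentation of the invitation cards".
- **Other records.** Section 2.5.e plans a tablet intake on arrival. It captures message type, times, whether the man stayed to be tested, and HIV status. Section 2.5.d has a counsellor take consent and carry out the rapid test, and section 3.1 requires signed consent. Section 2.5.a gives each card a unique code.

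The plan does not say who completes the intake, whether the counsellor records the card code, which record defines the primary outcome, or how the records are compared. It describes no blinding of those who record the outcome and no count of cards issued and left over.

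**The concern.** The recruiter role cannot be blind, because it reads out the allocated message. The same role produces the two counts whose ratio is the primary outcome. If entries were more complete, or more generous, under one message than the other, the error would pass straight into the arm comparison. The logistic model in 2.5.g adjusts for distributor, but that does not remove an error that differs by arm within the same distributor.

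The denominator is the more exposed half. A man who tests leaves an intake record, a consent form and a test result. A man who takes a card and never comes leaves nothing except the recruiter's delivery entry. If that entry is not made, uptake rises and no other planned record shows it.

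The numerator has a further looseness. The outcome is named as testing, yet it is measured through presentation of a card, and section 2.5.e itself allows for men who present and do not stay to be tested.

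**Working it through.** **Inputs (section 2.5.f unless noted)**
- "Power calculations assumed 8 percent HIV testing uptake among men in the control group".
- Intraclass correlation: 0.02.
- Size: 40 days at 100 cards per day, 4,000 men in all.
- Target: "we will have 80 percent power to detect a difference in HIV testing between groups of at least 5 percentage points", so 8% against 13%.
- Section 2.5.a: "an equal number of clinic days at each location within KMP are assigned to each study group", so 20 days and 2,000 men per arm.
- Assumed: two-sided 5% significance. The documents state neither level nor sidedness.

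**The plan's own figure**
- Design effect: 1 + (100 − 1) × 0.02 = 2.98.
- Effective size per arm: 2,000 / 2.98 = 671.1.
- Normal approximation without continuity correction: power 84.9%.
- With continuity correction: 629 men per arm before clustering. 629 × 2.98 / 100 = 18.7 days; adding one day per arm gives 19.7, rounded up to 20, or 40 days in all. On this basis power is 80.6%.

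The stated 80% is reproduced and is not in dispute.

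**Expected daily counts**
- Control: 100 × 0.08 = 8 men. U=U: 100 × 0.13 = 13 men.
- One man per day is 1/100 = 1 percentage point, and 1/5 = 20% of the target difference.
- One man is 1/8 = 12.5% of a control day's count and 1/13 = 7.7% of a U=U day's.

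**Numerator error in one arm only (hypothetical rates)**

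The documents give no error rate. The figures below use the normal approximation with variance inflated by 2.98, so they describe an analysis that allows for clustering.

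| Scenario | Observed difference | Chance of a significant result |
|---|---|---|
| No true effect, 10% missed in control | 0.8 points | 8.6% |
| No true effect, 1 man per day added in one arm | 1.0 point | 10.1% |
| No true effect, 2 men per day added in one arm | 2.0 points | 24.9% |
| 8% v 13%, full capture | 5.0 points | 84.9% |
| 8% v 13%, 10% missed in U=U only | 3.7 points | 62.4% |
| 8% v 13%, 10% missed in both arms | 4.5 points | 80.5% |

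Example, second row: standard error = √[(0.08 × 0.92 + 0.09 × 0.91) × 2.98 / 2,000] = 0.0152; 0.01 / 0.0152 = 0.66 standard errors; the two-sided rejection rate is 10.1%.

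**Denominator error (hypothetical: 10 non-returning cards per day not logged)**
- Control day: 8/90 = 8.9% instead of 8.0%. U=U day: 13/90 = 14.4% instead of 13.0%.
- Control only: 13.0 − 8.9 = 4.1 points. U=U only: 14.4 − 8.0 = 6.4 points.
- Both arms: 14.4 − 8.9, about 5.6 points. The ratio of the two uptakes is unchanged, and with no true effect the difference stays at zero.

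**The case against.** The best reply is that the recruiter's log does not stand alone. For each man who tests, the plan produces a coded card, a tablet intake with test status, a signed consent and a result from a counsellor. A tester invented by a recruiter would have no matching consent or result, and a missed one could be recovered. This stands in large part for the numerator: a reader might infer that recording errors could never be detected, and the documents do not support that. It is not a full answer. The intake follows card presentation and records message type, its completer is not named, and no comparison of records is planned. It does not touch the denominator.

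A reader might also infer that recruiters must record presentations while still away handing out cards, as if in two places at once. No section says so. Section 2.2 stations recruiters at the clinic sites, the synopsis refers to them in the plural, and the person handing out a card need not be the one who receives it. The visibility field shows only that some cards may be given out of sight of the van. Even if recruiters were absent at times, about 100 cards go out on every day in both arms, so absence alone need not differ by arm. Equal proportional losses dilute a true effect slightly and create no false one.

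Finally, the error rates above are invented for scale. That is correct, and they should be read that way.

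**Conclusion.** The point holds as a weakness in how the primary outcome is sourced, not as evidence of bias. One arm-aware role records the presentations and the deliveries. The better record of testing is already planned but not designated, and the denominator has no independent check.

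Daily counts of about 8 and 13 make the comparison sensitive. One man per day in one arm only is worth 1 percentage point, or 20% of the target difference. With no true effect, that would about double the false-positive rate, from 5% to 10.1%. These sizes rest on assumed error rates, on error confined to one arm, on 100 cards per day, and on the plan's 8%, 5-point and 0.02 assumptions. The power statement is unaffected.

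This is a cheap improvement that should be made before recruitment. An unlogged card that never returns cannot be recovered afterwards.

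**What to change.** Amend sections 2.5.d, 2.5.e and 2.5.g:

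1. **Numerator.** The counsellor enters the card's unique code with the test result in the planned tablet or test record. Define the primary numerator as a completed test in that record, and state how a man who tests without his card is counted.
2. **Denominator.** Use the coded cards issued to recruiters at the start of the day minus the unused cards handed back.
3. **Recruiter's log.** Keep it for delivery time and line of sight, and reconcile it each day with the card count and the intake.

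The cost is a protocol wording change, a few seconds per test and a daily card count, all by existing staff. The counsellor may still see which card is presented, so assessment is not fully blinded. What the change does is move the outcome to a completed test entered by someone other than the recruiter, and give the denominator a check that it now lacks.
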